4.0 Study Objective

Period 1

Primary Objective

1. To compare the efficacy of upadacitinib 15 mg QD and 30 mg QD versus placebo and versus adalimumab (ADA) for the treatment of signs and symptoms of PsA in subjects with moderately to severely active PsA who have an inadequate response or intolerance to 1 or more non-biologic DMARD (DMARD-IR).

Secondary Objective

- 2. To compare the efficacy of upadacitinib 15 mg QD and 30 mg QD versus placebo for the prevention of structural progression in subjects with moderately to severely active PsA who have an inadequate response or intolerance to 1 or more non-biologic DMARD (DMARD-IR).
- 3. To compare the safety and tolerability of upadacitinib 15 mg QD and 30 mg QD versus placebo and versus adalimumab in subjects with moderately to severely active PsA who and have an inadequate response or intolerance to 1 or more non-biologic DMARD (DMARD-IR).

[figure not shown]
Period 2

To evaluate the long-term safety, tolerability and efficacy of upadacitinib 15 mg QD and 30 mg QD in subjects with PsA who have completed Period 1.

5.0 Investigational Plan

5.1 Overall Study Design and Plan: Description

This is a Phase 3 multicenter study that includes two periods. Period 1 is 56 weeks in duration and includes a 24-week randomized, double-blind, parallel-group, placebo-

[figure not shown]
controlled and active comparator-controlled period followed by an additional 32 weeks of blinded, active comparator-controlled treatment (Weeks 24 – 56). Period 1 is designed to compare the safety, tolerability, and efficacy of upadacitinib 15 mg QD and 30 mg QD versus placebo and versus adalimumab 40 mg eow for the treatment of signs and symptoms of subjects with moderately to severely active PsA and have an inadequate response or intolerance to non-biologic DMARDs (DMARD-IR). Period 1 is also designed to compare the efficacy of upadacitinib 15 mg QD and 30 mg QD versus placebo for the prevention of structural progression. Period 2 is an open-label (blinded until the last subject completes the last visit of Period 1), long-term extension of up to a total treatment duration of approximately 5 years to evaluate the safety, tolerability and efficacy of upadacitinib 15 mg QD and 30 mg QD in subjects with PsA who have completed Period 1.

Upon approval of protocol amendment 7, subjects receiving upadacitinib 30 mg QD will be switched to upadacitinib 15 mg QD at their next scheduled study visit.

The study is designed to enroll approximately 1640 subjects at approximately 350 study centers worldwide to meet scientific and regulatory objectives without enrolling an undue number of subjects in alignment with ethical considerations.

The study duration will include a 35-day screening period; a 56-week blinded period which includes 24 weeks of double-blind, placebo-controlled and active comparator-controlled treatment followed by 32 weeks of active comparator controlled treatment (Period 1); a long-term extension period of up to a total treatment duration of approximately 5 years ([blinded until the last subject completes the last visit of Period 1] Period 2); a 30-day follow-up call or visit; and a 70-day follow-up call.

Subjects who meet eligibility criteria will be stratified by extent of psoriasis (\geq 3% body surface area [BSA] or < 3% BSA), current use of at least 1 DMARD, presence of dactylitis, and presence of enthesitis, except for subjects from China and Japan, where randomization for each country will be stratified by extent of psoriasis (\geq 3% body

surface area [BSA] or < 3% BSA) only, and then randomized in a 2:2:2:1:1 ratio to one of five treatment groups:

Group 1: Upadacitinib 15 mg QD (N = 410)

Group 2: Upadacitinib 30 mg QD (N = 410)

Group 3: ADA (40 mg every other week [eow]) (N = 410)

[figure not shown]
Group 4: Placebo followed by upadacitinib 15 mg QD (N = 205)

Group 5: Placebo followed by upadacitinib 30 mg QD (N = 205)

No more than approximately 15% of subjects will be enrolled with concomitant use of HCQ, sulfasalazine, bucillamine, or iguratimod.

Subjects will receive both oral study drug QD (upadacitinib 15 mg, upadacitinib 30 mg, or matching placebo) and subcutaneous study drug eow (either ADA 40 mg or matching placebo) until all subjects have completed Period 1 (Week 56) and sites and subjects are unblinded to study treatment.

Subjects who were assigned to placebo at Baseline will be preassigned to receive either upadacitinib 15 mg QD or upadacitinib 30 mg QD starting at Week 24 in a 1:1 ratio. Subjects who complete the Week 56 visit (end of Period 1) will enter the long-term extension portion of the study, Period 2 (total treatment up to approximately 5 years). Subjects will continue study treatment as assigned in Period 1. Subjects who are assigned to the upadacitinib 15 mg QD, upadacitinib 30 mg QD, or adalimumab 40 mg eow will continue to receive upadacitinib 15 mg QD, upadacitinib 30 mg QD, or adalimumab 40 mg eow, respectively, in a blinded manner. When the last subject completes the last visit of Period 1 (Week 56), study drug assignment in both periods will be unblinded to the sites, and subjects will be dispensed study drug in an open-label fashion until the completion of Period 2. Upon approval of protocol amendment 7, subjects receiving

[figure not shown]

upadacitinib 30 mg QD will be switched to upadacitinib 15 mg QD at their next scheduled study visit.

Subjects must have had inadequate response to ≥ 1 non-biologic DMARD (MTX, SSZ, LEF, cyclosporine, apremilast, bucillamine or iguratimod) or an intolerance to or contraindication for DMARDs as defined by the investigator prior to the Screening visit. No background non-biologic DMARD therapy is required during participation in this study. For subjects who are on non-biologic DMARD therapy at baseline (MTX, SSZ, LEF, apremilast, hydroxychloroquine (HCQ), bucillamine or iguratimod), non-biologic DMARDs should have been started ≥ 12 weeks prior to the baseline visit, must be at stable dose for ≥ 4 weeks prior to the first dose of study drug and remain at stable dose through Week 36 of the study; the non-biologic DMARD dose may be decreased only for safety reasons. In addition, all subjects taking MTX should take a dietary supplement of oral folic acid (or equivalent) throughout study participation. Folic acid dosing and timing of regimen should be followed according to the Investigator's instructions. Please refer to Section 5.2.3.2 for additional details related to prior and concomitant DMARD therapy.

At Week 16, rescue therapy will be offered to subjects classified as non-responders (defined as not achieving at least 20% improvement in either or both tender joint count (TJC) and swollen joint count (SJC) at both Week 12 and Week 16) as follows: 1) add or modify doses of non-biologic DMARDs, NSAIDs, acetaminophen/paracetamol, low potency opioid medications (tramadol or combination of acetaminophen and codeine or hydrocodone), oral corticosteroids and/or 2) receive 1 intra-articular, trigger point or tender point, intra-bursa, or intra-tendon sheath corticosteroid injection for 1 peripheral joint, 1 trigger point, 1 tender point, 1 bursa, or 1 enthesis as described in Section 5.2.3.4 (Rescue Therapy).

After the last subject completes the Week 24 study visit, an unblinded analysis will be conducted for the purpose of initial regulatory submission. To maintain integrity of the trial during the blinded 56-week period study sites and subjects will remain blinded until all subjects have reached Week 56. A second unblinded analysis may be conducted for

regulatory purposes after all subjects have completed Period 1. A final analysis will be conducted after all subjects have completed Period 2.

Starting at Week 36, subjects who fail to demonstrate at least 20% improvement in either or both TJC and SJC compared to baseline at 2 consecutive visits will be discontinued from study drug treatment. Additionally, in subjects continuing on study drug, starting at the Week 36 visit (after Week 36 assessments have been performed), initiation of or change in background PsA medication(s) including, oral corticosteroids, non-steroidal anti-inflammatory drugs (NSAIDs), acetaminophen/paracetamol, low potency opiates, and non-biologic DMARDs (concomitant use of up to 2 non-biologic DMARDs except the combination of MTX and leflunomide) is allowed as per local label with maximum doses as outlined in Section 5.2.3.3.

Each subject will undergo a maximum of 6 scheduled visits for x-ray examination of bilateral hands and feet (unless unscheduled repeat imaging is needed due to failure to meet the quality requirements) at Screening, Week 24, Week 56, Week 104, Week 152, and Week 260/Premature discontinuation.

[figure not shown]
All subjects who fail to attain at least a 20% improvement in either or both TJC and SJC at Week 12 and Week 16 will have an x-ray examination at Week 16. All subjects will receive x-rays of hands and feet if they discontinue from the study or from study drug at Week 12 or later and it has been at least 12 weeks from when x-rays were last obtained during Period 1 or at least 24 weeks during Period 2.

X-rays of the hands and feet will be sent to the central imaging vendor designated by the Sponsor. Images should be reviewed by the investigator to assess for clinically significant findings. The x-rays will not be assessed by the central imaging vendor for any clinically significant findings that may impact a subject's health.

A schematic of the overall study design is shown in Figure 1 below.

Figure 1. Study Design

N=1640

- a. All subjects will receive x-rays of hands and feet at Screening, Wk 24, Wk 56, Wk 104, 152, and Wk 260/PD.
- b. At Week 16 rescue therapy will be offered to, subjects classified as non-responders (defined as not achieving at least 20% improvement in either or both tender joint count (TJC) and swollen joint count (SJC) at both Week 12 and Week 16) as described in Section 5.2.3.4.
- c. At Week 24, all placebo subjects will switch to upadacitinib 15 mg QD or 30 mg QD (1:1 ratio) regardless of response.

Note: Upon approval of protocol amendment 7, subjects receiving upadacitinib 30 mg QD will be switched to upadacitinib 15 mg QD at their next scheduled study visit.

Additionally, an unblinded interim analysis will be conducted by an independent external Data Monitoring Committee (DMC) after approximately 600 subjects have completed the Week 12 visit or have prematurely discontinued from the study. The interim analysis is to assess if the study met the pre-defined No-Go boundary for the primary endpoint ACR20. Details of the interim analysis and decision criteria will be specified in a separate DMC charter.

[figure not shown]
ABT-494
M15-572 Protocol Amendment 8
EudraCT 2016-004130-24

Screening Period

Within 35 days prior to the Baseline Visit, subjects will receive a full explanation of the study design and study procedures, provide a written informed consent, and undergo the screening procedures outlined in Appendix C. Lab values can be re-tested once during the screening period. If the re-tested lab value(s) remain(s) exclusionary, the subject will be considered a screen failure. If the subject does not have either an elevated hs-CRP or an erosion on x-ray examination of bilateral hands and feet (inclusion criterion 4), hs-CRP may be re-tested once during the screening period. Redrawing samples if initial samples were unable to be analyzed would not count as a retest since initial result was never obtained.

Subjects that initially screen fail for the study are permitted to re-screen once following re-consent without prior AbbVie approval. For additional re-screening, AbbVie Therapeutic Area Medical Director (TA MD) approval is required. All screening procedures with the possible exceptions noted below will be repeated during re-screening. The subject must meet all the inclusion and none of the exclusion criteria at the time of rescreening in order to qualify for the study. There is no minimum period of time a subject must wait to re-screen for the study.

If the subject had a complete initial screening evaluation including HBV, HCV and HIV serology, the assessment of an Interferon-Gamma Release Assay (IGRA; QuantiFERON Tuberculosis [TB] Gold test) and/or a purified protein derivative (PPD) test (or equivalent) (or both if required per local guidelines), ANA, chest x-ray, and electrocardiogram (ECG), these tests will not be required to be repeated for re-screening provided the conditions noted in Section 5.3.1.1 are met, there are no changes in the subject's medical history that would warrant re-testing, and no more than 90 days have passed. Provided the conditions noted in the central imaging manual are met, if the subject had x-rays of hands and feet performed within 12 weeks of re-screening these tests will not be required for re-screening.

Period 1 (56-Week Randomized, Double-Blind Treatment Period)

Period 1 will begin at the Baseline Visit (Day 1) and will end at the Week 56 Visit. At the Baseline Visit, subjects who meet all the inclusion criteria and none of the exclusion criteria described in Section 5.2.1 and Section 5.2.2 will be enrolled into the study and randomized to double-blind treatment. During this period of the study, subjects will visit the study site at Baseline (Day 1), Weeks 2, 4, 8, 12, 16, 20, 24, 28, 32, 36, 44 and 56. A \pm 3 day window is permitted around scheduled study visits up to Week 36. Following Week 36, a \pm 7 day window is permitted. The last dose of oral study drug in Period 1 is taken the day prior to the Week 56 visit.

[figure not shown]
Period 2 (Long-Term Extension Period [Up to a Total Treatment Duration of Approximately 5 Years])

Period 2 will begin at the Week 56 visit after all assessments have been completed. When the last subject completes the last visit of Period 1 (Week 56), study drug assignment in both periods will be unblinded to the sites, and subjects will be dispensed study drug in an open-label fashion until the completion of Period 2. During Period 2, subjects will have a study visit at Week 56 and every 12 weeks thereafter until completion of the study. A \pm 7 day window is permitted around scheduled study visits. The last dose of oral study drug is taken the day prior to the Week 260 visit.

Upon approval of protocol amendment 7, subjects receiving upadacitinib 30 mg QD will be switched to upadacitinib 15 mg QD at their next scheduled study visit.

Discontinuation of Study Drug and Continuation of Study Participation (Period 1 and Period 2)

Starting at Week 36, subjects who failed to show at least 20% improvement in either or both TJC and SJC compared to baseline at 2 consecutive visits will be discontinued from study drug treatment. Subjects who discontinue study drug treatment may choose to continue to participate in the study (refer to Section 5.4.1 for additional details). Subjects who prematurely discontinue study drug should complete a Premature Discontinuation

[figure not shown]
visit (PD visit) as soon as possible, preferably within 2 weeks of study drug discontinuation and preferably prior to initiation of another therapy. Afterwards, subjects should follow the regular visit schedule as outlined in Appendix C and adhere to all study procedures except for dispensing study drug, annual TB testing, PK sample collection, blood sample collection for optional exploratory research and validation studies, and calculation for drug assignment based on TJC/SJC. If a subject no longer wants to provide assessments (withdrawal of informed consent) following discontinuation of study drug, a second PD visit is not required.

Premature Discontinuation of Study (Withdrawal of Informed Consent) (Period 1 and Period 2)

Subjects may withdraw from the study completely (withdrawal of informed consent) for any reason at any time (refer to Section 5.4.2 for additional details). If a subject prematurely discontinues study drug treatment and study participation (withdrawal of informed consent), the procedures outlined for the Premature Discontinuation visit (PD visit) should be completed as soon as possible, preferably within 2 weeks of study drug discontinuation and preferably prior to initiation of another therapy. In addition, a 30-day follow-up visit (or phone call if a visit is not possible) should occur to determine the status of any ongoing AEs/SAEs or the occurrence of any new AEs/SAEs. For subjects on subcutaneous study drug, a 70-day follow-up phone call should occur to determine the status of any ongoing AEs/SAEs or the occurrence of any new AEs/SAEs. The 70-day follow-up phone call will not be required for any subject that initiates commercial adalimumab. Subjects who discontinue from the study will not be replaced.

Follow-Up Period

Subjects who complete the last visit of Period 2 (Week 260) will have a follow-up visit/phone call approximately 30 days after the last dose of oral study drug to obtain additional safety information. Whenever laboratory results are needed for AE follow-up, the 30-day follow-up should be performed as a visit at the site. A follow-up phone call will also occur 70 days after the last administration of injectable study drug to determine

the status of any ongoing AEs/SAEs or the occurrence of any new AEs/SAEs. Subjects completing the study on open label (OL) therapy will only be required to have the 30-day follow-up visit/phone call if on oral study drug or the 70-day follow-up phone call if on injectable study drug. The follow-up visit/phone call is not applicable for subject who begin commercially available upadacitinib or adalimumab. The 30-day follow-up visit/phone call and 70-day follow-up call are not required for subjects who discontinued study drug and continued study participation with completion of at least one study visit approximately 30 days or 70 days after last dose of study drug, respectively. For subjects who enter CTTP, the 30-day follow-up visit/phone call following the last dose of study drug at the Week 260 visit will not be required.

[figure not shown]

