5.3 Efficacy and Safety Assessments/Variables

5.3.1 Efficacy and Safety Measurements Assessed

[figure not shown]
Subjects will be allowed a visit window of \pm 3 days for all study visits (with the exception of the Baseline Visit, as the screening window is a maximum of 35 days) up to the Week 36 visit. Visits after the Week 36 visit will have a visit window of \pm 7 days.

If a subject has an out of window visit, the next visit should occur as originally scheduled based on the first date of study drug administration (Baseline Visit).

Study procedures described are listed in the following section of this protocol and are summarized in tabular format in Appendix C.

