For subjects who re-screen: Provided the conditions outlined in the imaging manual are met, if the subject had x-rays of hands and feet performed within 12 weeks of re-screening these tests will not be required for re-screening.

Radiographs will be sent to the designated central imaging vendor and will be interpreted by an experienced reader selected for the study, who will make the final determination as to whether a subject has at least 1 erosion. The imaging vendor will return an eligibility notification report to the site as outlined in the central imaging documents.

Further details regarding the specific imaging techniques to be used will be provided in an imaging manual from AbbVie or designee.

[figure not shown]
The Investigator or their qualified delegate should read the Screening visit x-rays of the hands and feet to determine if the subject fulfills item 5 of the CASPAR criteria (Appendix G). It is the responsibility of the Investigator to ensure that all delegates are qualified and that all training is documented.

In the event Hand and Feet x-rays may not be performed at the planned visit due to a state of emergency or pandemic situation, perform the Hand and Feet x-rays at the next feasible visit.

Chest X-Ray (CXR)

A CXR (posterior-anterior and lateral views) is required:

• For all subjects at Screening to rule out the presence of TB or other clinically relevant findings. The CXR will not be required if the subject had a previously normal CXR (posterior-anterior and lateral views) within 90 days of Screening, provided all source documentation is available at the site as

outlined below and provided nothing has changed in the subject's medical history to warrant a repeat test.

• Annually for subjects with one or more TB risk factors as identified by the TB risk assessment form (Appendix E), subjects living in areas endemic for TB, and subjects with newly positive PPD and/or QuantiFERON-TB Gold test or equivalents after baseline.

Subjects can have a repeat CXR at any time during the study as warranted based on the opinion of the Investigator.

[figure not shown]

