
b. Day of first dose of study drug.

Table 2. Analysis Windows for Efficacy Analysis for Period 1 (for SF-36, EQ-5D-5L, FACIT-F, WPAI, BASDAI, HRU and Derived Endpoints^a)

Protocol Specified Visit Week	Lower Bound	Target Day	Upper Bound
Baseline	-99	1 ^b	1
12	2	85	127
24	128	169	Min (211, first dose date from Week 24 dispensed kit)
36	Min (211, first dose date from Week 24 dispensed kit) + 1	253	323
56	324	393	435

a. PASDAS, BASDAI 50 response rates, Change from baseline in Morning stiffness (mean of BASDAI Questions 5 and 6), ASDAS, proportion of subjects with ASDAS Inactive Disease, proportion of subjects with ASDAS Major Improvement, proportion of subjects with ASDAS Clinically Important Improvement.

Table 3. Analysis Windows for Safety Analysis for Period 1 (for Total Cholesterol, HDL-C, LDL-C, Triglycerides)

Protocol Specified Visit Week	Lower Bound	Target Day	Upper Bound
Baseline	-99	1 ^a	1
4	2	29	57
12	58	85	127
24	128	169	Min (211, first dose date from Week 24 dispensed kit)

a. Day of first dose of study drug.

b. Day of first dose of study drug.

Table 4. Analysis Windows for Efficacy Analysis for Period 1 (for BSA-Psoriasis, PASI, sIGA, LDI, LEI, SPARCC Enthesitis Index and Derived Endpoints^a)

Protocol Specified Visit Week	Lower Bound	Target Day	Upper Bound
Baseline	-99	1 ^b	1
12	2	85	99
16	100	113	141
24	142	169	Min (211, first dose date from Week 24 dispensed kit)
36	Min (211, first dose date from Week 24 dispensed kit) + 1	253	323
56	324	393	435

a. MDA, dactylitis count/total enthesitis count, proportion of subjects with resolution of dactylitis/enthesitis (out of all sites, or the sites included in SPARCC or LEI), PAISI75/90/100, proportion of subjects achieving a static Investigator Global Assessment of psoriasis (sIGA) score of 0 or 1 and at least a 2-point improvement from baseline.

Table 5. Analysis Windows for Efficacy Analysis for Period 1 (for SAPS)

Protocol Specified Visit Week	Lower Bound	Target Day	Upper Bound
Baseline	-99	1 ^a	1
16	2	113	141
24	142	169	Min (211, first dose date from Week 24 dispensed kit)
36	Min (211, first dose date from Week 24 dispensed kit) + 1	253	323
56	324	393	435

a. Day of first dose of study drug.

b. Day of first dose of study drug.

Table 6. Analysis Windows for Efficacy Analysis for Period 1 (for X-Rays of Hands and Feet)

Protocol Specified Visit Week	Lower Bound	Target Day	Upper Bound
Baseline	-99	1ª	1
16 ^b	2	113	141
24	142	169	197
36°	198	253	323
56	324	393	435

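### The SAP's baseline x-ray window opens at Day -99, but the re-screening rule can admit a hand and foot film from as early as Day -119, so a usable pre-dose film may fall in no analysis window

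*Protocol*

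**What the plan says.** **Reuse of films.** Protocol 5.1 (Screening Period) provides that "if the subject had x-rays of hands and feet performed within 12 weeks of re-screening these tests will not be required for re-screening". Protocol 5.3.1.1 (X-Rays of the Hands and Feet) repeats the rule. Both places make it conditional; 5.1 puts it as "Provided the conditions noted in the central imaging manual are met".

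**Length of screening.** Screening falls within 35 days before the Baseline Visit (Protocol 5.1), and Protocol 5.3.1 confirms that "the screening window is a maximum of 35 days". On when re-screening may start, Protocol 5.1 says: "There is no minimum period of time a subject must wait to re-screen for the study".

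**Film schedule.** Appendix C schedules hand and foot films at Screening and then not before Week 16 (subjects meeting the rescue criteria) or Week 24 (everyone). None is scheduled at the Baseline Visit.

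**Analysis window.** The x-ray windows are in the SAP 5.2 table headed "Table 6. Analysis Windows for Efficacy Analysis for Period 1 (for X-Rays of Hands and Feet"). Its Baseline row runs from Day -99 to Day 1, and the next window opens at Day 2.

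**Use of the window.** SAP 9.2.3 analyses change from baseline in SHS at Week 24 by ANCOVA with baseline SHS as covariate. Missing Week 24 scores are predicted from the scores in the baseline and Week 16 windows. This is ranked key secondary endpoint 4 and carries the structural-progression objective.

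**The concern.** The protocol's time limit on a reused film runs back from re-screening, whereas the SAP's limit runs back from first dose. The two were not reconciled, and the SAP bound is the tighter one when the second screening is long and the film is old.

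For most assessments this would not matter, because they are repeated at the Baseline Visit. Hand and foot films are not: the Screening film, or a reused one, is the only pre-dose film. If it falls outside the window, the SAP states no fallback. Change from baseline and the ANCOVA covariate are then both undefined, and linear extrapolation has no starting point. The as-observed analysis needs the same baseline. The multiple-imputation code in SAP Appendix D lists the baseline value among its variables and might fill it in, but that is a sensitivity analysis only.

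At stake is the loss of eligible, treated subjects from SHS, erosion and joint-space-narrowing change scores because of a date bound, although a film exists.

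**Working it through.** **Inputs**
- Maximum age of a reused film at re-screening: 12 weeks = 84 days (Protocol 5.1 and 5.3.1.1).
- Maximum interval from re-screening to Baseline: 35 days (Protocol 5.1 and 5.3.1).
- Day convention: first dose is Day 1 and there is no Day 0, so a date k days before first dose is Day -k (SAP 5.2).
- Baseline x-ray window: Day -99 to Day 1 (SAP Table 6).
- SHS power statement: about 90% for a standardized effect of 0.26, two-sided alpha 0.025, 10% dropout (SAP 4.3), with 410 per upadacitinib dose and 205 + 205 = 410 on placebo.

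**Date arithmetic**
- Oldest film the protocol text admits: 35 + 84 = 119 days before first dose, i.e. Day -119.
- Uncovered band: Day -119 to Day -100, which is 119 - 99 = 20 days.
- Re-screening on Day -15: 15 + 84 = 99, so every reusable film is inside the window.
- Re-screening on Day -16: 16 + 84 = 100, so the gap opens here.
- Re-screening on Day -35: a film 64 days old at re-screening is just inside (35 + 64 = 99); films 65 to 84 days old are outside.

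A subject is affected only if re-screened, not re-imaged, re-screened at least 16 days before Baseline, and holding a film old enough to reach Day -100.

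**The plan's own power figure**
- Evaluable subjects per arm: 410 x 0.90 = 369.
- Power = Phi(0.26 x sqrt(369/2) - 2.2414) = Phi(3.5316 - 2.2414) = Phi(1.2902) = 90.15%, which reproduces the stated figure.

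**Effect of losing subjects.** The documents give no rate, so these fractions of evaluable subjects per arm are assumptions:

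| Fraction lost | n per arm | Power |
|---|---|---|
| 0.5% | 367.2 | 90.0% |
| 1% | 365.3 | 89.8% |
| 2% | 361.6 | 89.5% |
| 5% | 350.6 | 88.5% |

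**The case against.** **The imaging manual may close the gap.** Reuse depends on conditions in a document that is not available, and it could limit film age relative to Baseline. This stands: the gap is in the two documents as written, and nothing shows that any subject fell into it.

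**The 12 weeks might be counted from Baseline.** The oldest film would then be Day -84 and there would be no gap. The text counts from re-screening, so this is the less natural reading.

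**Day -99 may be a generic cut-off.** The same bound appears in SAP Tables 2 to 5, for assessments first scheduled at Baseline, where a 99-day look-back does little; in Table 1 the lower bound is blank. Protocol 8.1.3 and 8.1.5.3 define baseline as pre-dose data with no lower limit. Programmers may therefore have taken any pre-dose film. That is plausible, but those protocol definitions cover baseline summaries, laboratory data and vital signs. For x-rays, the SAP prints a day bound and does not say that it is nominal.

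**The missing-joint rule.** A reader might infer from SAP 9.4.25 that every joint would count as missing at Baseline and drop out of SHS at all visits. The text does not support this. That rule concerns joints without a score within a reading session, and a film that was read has joint scores whatever its date. The loss follows only from the window, through the baseline-window wording in SAP 9.2.3.

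**The key analyses are done.** SAP 11.1 says that the primary efficacy analysis and Period 1 reporting are complete and that version 4.0 governs only future long-term reporting. Appendix F dates the Week 24 lock to January 2020. This stands, and it limits the fix.

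**Conclusion.** The inconsistency is real on the face of the documents: up to 20 days of films that the protocol text can admit fall in no SAP window, and no fallback is stated. It rests on counting the 12 weeks from re-screening, on an imaging manual that sets no tighter limit, and on Table 6 being applied as printed.

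Its size is probably small. The number affected is unknown, and even an assumed 5% loss leaves 88.5% power.

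A reader might infer that the SHS comparison is biased, or that its power is fragile. Neither is supported. The age of the film is fixed before randomization, so treatment cannot cause this missingness, and the power figures move little. What remains is an avoidable loss of data and precision on a ranked endpoint and on its continuing long-term follow-up.

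**What to change.** **Remaining long-term SHS reporting.** In SAP Table 6, define baseline SHS as the last readable film on or before the first dose, or set the lower bound at Day -119 or earlier. Use actual film dates wherever time enters a model, since an older film lengthens the interval to follow-up. If Day -99 was meant only as a nominal limit, say so.

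**Completed Week 24 and Week 56 analyses.** Count, by treatment group, the subjects whose only pre-dose film precedes Day -99 and report how they were handled. If any were excluded, add a supplementary analysis that includes them. Do not redefine the completed ranked analysis: changing the baseline of a multiplicity-controlled endpoint after unblinding would be post hoc. Capping the age of reused films would not help either, because enrolment is complete.

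**Cost.** One table cell, a short query on film dates and, only if subjects were excluded, one extra analysis.
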